11.5. Immunogenicity Analyses

No formal hypothesis on immunogenicity will be tested. Descriptive statistics (geometric mean and 95% CI for ELISA and virus neutralization assays; median and quartiles for ELISpot and intracellular cytokine staining [ICS]) will be calculated for continuous immunologic parameters at all timepoints. For the humoral assays, geometric mean fold rises from baseline and corresponding 95% CIs may be calculated as well. For immunogenicity, baseline is considered as the last assessment pre-vaccination with Ad26.RSV.preF or placebo. Graphical representations of immunologic parameters will be made as applicable.

Frequency tabulations will be calculated for discrete (qualitative) immunologic parameters as applicable.

The primary analysis set for immunogenicity is the PPI set. As a sensitivity analysis, key tables will also be based on the FA set. Depending on their occurrence, the effect of missed doses or natural infections might be further explored. Note that they will be included in the tables showing the FA set.

11.6. Efficacy versus Immunogenicity Relationship

The relationship between immunogenicity parameters and the VL-AUC as measured by RT-PCR and the AUC for clinical symptoms will be graphically explored.

11.7. Safety Analyses

No formal statistical testing of safety data is planned. All safety data will be analyzed descriptively by regimen.

Adverse Events

The verbatim terms used in the eCRF by investigators to identify AEs will be coded using the Medical Dictionary for Regulatory Activities (MedDRA). All reported AEs with onset during the

active phases (ie, AEs emerging after vaccination up to 28 days post-vaccination or during the quarantine phase), and all SAEs, will be included in the analysis. For each AE, the percentage of subjects who experience at least one occurrence of the given event will be summarized by group separately for the vaccination phase and challenge phase.

Summaries, listings, datasets, or subject narratives may be provided, as appropriate, for those subjects who die, who discontinue study vaccine due to an AE, or who experience a severe AE or an SAE.

Summaries and/or listings may be provided separately for AEs with onset outside the active phases.

Solicited local (at injection site) and systemic AEs will be summarized descriptively. The overall frequencies per vaccine group as well as frequencies according to severity and duration will be calculated for solicited AEs. In addition, the number and percentages of subjects with at least one solicited local (at injection site) or systemic AE will be presented. Frequencies of unsolicited AEs, separately for all and vaccination-related only, will be presented by System Organ Class and preferred term. Unsolicited AEs will be presented separately for vaccination phase and quarantine phase.

Clinical Laboratory Tests

Laboratory abnormalities will be determined according to the FDA Guidance document (see [Attachment 1](#)), or in accordance with the normal ranges for the clinical laboratory parameter if no grades are available. If a laboratory value falls within the grading as specified in the FDA table, but also within the laboratory normal limits, the value is considered as normal. Emerging abnormalities will be tabulated.

Vital Signs

A tabulation of the distribution of temperatures per half-degree intervals will be provided. For systolic and diastolic blood pressures, heart rate and respiratory rate, the percentage of subjects with values beyond clinically relevant limits will be summarized.

Electrocardiogram

Any abnormalities in ECG parameters (at screening and on admission to the Unit) will be listed.

Physical Examination

Any abnormality in physical examination considered to be clinically significant will be captured as an AE and shown in the AE outputs. Therefore, no separate analysis will be done.

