All subjects will stay in the quarantine Unit from 1 or 2 days prior to RSV inoculation until 12 days after challenge. Nasopharyngeal swabs will be tested for the presence of virus prior to discharge using rapid virus antigen test (RVAT). Subjects will only be discharged when no detectable virus is present (negative RVAT). If symptoms are present, but no virus is detected (negative RVAT), discharge will be at the investigator's discretion. If appropriate, subjects may reside in quarantine for an additional night or longer before discharge.

To reduce the risk of passing RSV on to others, the subject will be advised to avoid contact with the following vulnerable groups of people for two weeks after they leave the quarantine Unit:

- any person with any known immunodeficiency
- any person receiving immunosuppressant medications
- any person undergoing or soon to undergo cancer chemotherapy
- any person who has congestive heart failure or is in frail health
- any person who has a diagnosis of emphysema or chronic obstructive pulmonary disease (COPD), is elderly residing in a nursing home, or has severe lung disease
- any person who has received a transplant (bone marrow or solid organ)
- children below the age of 1 year
- elderly persons (aged 75 years or older).

Unknown Risks

There may be other serious risks that are not known.

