2.1.2. Endpoints

Primary Endpoint: Viral Load

The primary endpoint is the VL-AUC of RSV-A Memphis 37b as determined by quantitative RT-PCR assay of nasal wash samples.

Nasal wash samples are taken every 12 (± 1) hours beginning two days (ie, in the morning) after inoculation of the challenge virus. Quantitative RT-PCR is utilized to measure viral load.

Secondary Endpoints

- Peak viral load of RSV-A Memphis 37b, defined as the maximum viral load as determined by quantitative RT-PCR assay of nasal wash samples, observed over the entire time period.
- Occurrence of symptomatic RSV infection defined as two quantifiable RT-PCR measurements at different timepoints plus symptoms of any grade from two different categories from the subject symptom card (SSC)^a or two quantifiable RT-PCR measurements plus any Grade 2 symptom from any category. The three SSC categories are:
 - Upper Respiratory symptoms: runny nose, stuffy nose, sneezing, sore throat, earache

^a See [Attachment 3](#).

-
- Lower Respiratory symptoms: cough, shortness of breath, chest tightness, wheeze
 - Systemic symptoms: malaise, headache, muscle and/or joint ache, chilliness/feverishness
 - Occurrence of RSV infection defined as two quantifiable RT-PCR measurements plus any clinical symptom of any severity.
 - Total weight of mucus produced and tissue count.
 - Safety and tolerability
 - Unsolicited adverse events (AEs) from ICF signature until 28 days after vaccination, and from the entry into the Unit until 28 days after challenge.
 - Safety data including, but not limited to, physical examinations, vital signs, 12-lead electrocardiograms (ECGs) and clinical laboratory results (including biochemistry, hematology, and urinalysis).
 - Serious adverse events (SAEs) throughout the study (from signing the ICF to the end of the study, 6 months after vaccination).
 - Solicited local and systemic AEs for 7 days after vaccination.

Exploratory Endpoints

- AUC of the total clinical symptom score. The total clinical symptom score is a composite of 13 self-reported symptoms (on the SSC) divided into three categories (Upper Respiratory, Lower Respiratory, Systemic).
- The VL-AUC of RSV-A Memphis 37b, as determined by quantitative culture of RSV of nasal wash samples.

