9.1.5. Viral Challenge Phase

9.1.5.1. Entry to the Quarantine Unit

Subjects will enter the quarantine Unit either one or two days before the viral challenge, to acclimatize and perform entry assessments. The following assessments can take place on either day: complete physical examination, including body weight, relevant medical information since vaccination, vital signs and spirometry, samples for clinical laboratory tests (including cardiac enzymes), ECG, blood samples for immunogenicity assessments, spirometry, and recording of any unsolicited AEs/SAEs and concomitant medications. Nasopharyngeal swabs and nasal wash samples will be collected to screen for respiratory virus and for RSV pre-F antibody assessment, respectively, and blood samples will be taken to determine sero-susceptibility for RSV for post-hoc reconfirmation (neutralization assay).

The SSC will be filled out by the subject and reviewed by the attending physician. Tissues for tissue counts and mucus weight will be distributed on Day -1. The first 24-hour collection will start on Day -1; tissue counts and mucus weights will be determined on Day 0.

A serum pregnancy test (β -hCG) will be performed for all female subjects. A urine drug screen, a urine cotinine test, and an alcohol breath test will be performed.

Throughout the challenge phase of the study from entry to the Unit until discharge, subjects will stay in individual isolation rooms to minimize cross-contamination between subjects.

Before challenge inoculation on Day 0, the subject's clinical status will be checked, including any available laboratory results or receipt of additional medical records.

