9.2.6. Safety Evaluations

Any clinically relevant changes occurring from ICF signature until discharge from the Unit must be recorded on the eCRF. Any clinically significant abnormalities, including those persisting at the end of the study/early withdrawal, will be followed by the investigator until resolution or until a clinically stable endpoint is reached.

Adverse events occurring from ICF signature until 28 days after vaccination will be examined for relationship to study vaccine. Adverse events occurring from admission to the quarantine Unit until 28 days after challenge will be evaluated for relationship to the challenge.

The study will include the evaluations of safety and tolerability outlined in the following sections according to the timepoints provided in the [Time and Events Schedule](#).

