3.1.1. Phase definitions

The phases in the study will be constructed as follows:

Table 2: Phase Definitions

Phase	Phase #	Period	Period #	Interval	
				From	To
Screening	1			Date and time of signing the informed consent form ^a	One minute prior to start of post-dose period
Vaccination	2	Post-Dose	1	Date and time of vaccination	Minimum of: 
 23:59 on 32 days after the vaccination (23:59 of day of vaccination + 32 days) 23:59 at the date of database cut-off date in case of interim One minute prior to date and time of the challenge 23:59 at the date of last contact (for early discontinuation)
Follow-up Vaccination	3			One minute after Post-Dose period end	Minimum of: 
 23:59 at the date of last contact (for early discontinuation) 23:59 at the date of database cut-off date in case of interim One minute prior to Challenge
Challenge	4	Post-Challenge	2	Date and time of challenge (Study Day 0)	Minimum of: 
 Maximum (28 days after challenge at 23:59, scheduled visit 4 weeks after challenge at 23:59) 23:59 at the date of database cut-off date in case of interim 23:59 at the date of last contact (for early discontinuation)
Follow-up Challenge	5			One minute after Post-Challenge period end	Minimum of: 
 23:59 at the date of database cut-off date in case of interim 23:59 at the date of last contact. (for completed or discontinued subjects)

^a in case an earlier date is available (eg. for lab or vital signs), then use the very first date to include all data

The Follow-up Vaccination phase will only be created in case a subject was challenged to the later than 32 days after vaccination. Moreover, if for one subject no challenge was performed, the Follow-up Vaccination phase should be created and to capture any observations after the Vaccination phase.

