7.1. Adverse Events (AE)

7.1.1. Definitions

Solicited AEs, collected for 7 days after vaccination, shown in the tables are extracted from the diary pages of the CRF. For unsolicited AEs, only AEs with start date (grade and/or relation) within the 28-day period following vaccination or challenge will be presented in the safety tables except for SAE, which will be captured and tabulated in the outputs covering the whole study period. All other collected unsolicited adverse events will be presented through listings.

Solicited local AEs will be by definition considered as related to the study vaccine.

The severity of the AEs will be classified as grade 1 to 4. Solicited events that are graded less than grade 1, are not considered as AE. In case no grades are available, the grading of the solicited events will occur according to the grading list in [Attachment 1](#).

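### Neither Protocol 11.7 nor the SAP analyses unsolicited AEs over the whole window that the secondary safety endpoint sets around challenge

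*Protocol*

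**What the plan says.** **Endpoint and collection.** Protocol 2.1.2 defines the secondary safety endpoint as "Unsolicited adverse events (AEs) from ICF signature until 28 days after vaccination, and from the entry into the Unit until 28 days after challenge". Protocol 9.2.6 uses the same challenge-side span for attribution: "Adverse events occurring from admission to the quarantine Unit until 28 days after challenge will be evaluated for relationship to the challenge".

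**Protocol analysis.** Protocol 11.7 includes all SAEs, but other AEs only if their onset is in the "active phases (ie, AEs emerging after vaccination up to 28 days post-vaccination or during the quarantine phase". It adds: "Unsolicited AEs will be presented separately for vaccination phase and quarantine phase". Quarantine is the Unit stay: Protocol 9.1.5.1 writes "Throughout the challenge phase of the study from entry to the Unit until discharge", and Protocol 1.3.4 says "All subjects will stay in the quarantine Unit from 1 or 2 days prior to RSV inoculation until 12 days after challenge". Summaries of AEs outside the active phases are optional.

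**SAP analysis.** SAP 7.1.1 sets this rule for the unsolicited events: "only AEs with start date (grade and/or relation) within the 28-day period following vaccination or challenge will be presented in the safety tables". SAEs are exempt and are tabulated for the whole study; everything else goes to listings. SAP Table 2 (Section 3.1.1) starts the Challenge phase at inoculation. It ends the Post-Dose period at "23:59 on 32 days after the vaccination (23:59 of day of vaccination + 32 days", or one minute before challenge if that is earlier. SAP 7.1.3 allocates AEs to these periods by start date and time, and treats the follow-up phases as non-active.

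**Declared changes.** SAP Section 2 names the ECG tables and a sensitivity analysis of the primary endpoint. It does not mention AE windows.

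**The concern.** An endpoint defined over one window should be analysed over that window. Here two analysis sections each leave out a different piece of it, and nothing in the SAP says that it departs from the protocol.

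The two pieces matter for different reasons:

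- **After discharge.** From challenge to discharge, symptom-card findings above Grade 0 are not recorded as AEs unless serious (Protocol 9.2.4 and 12.3.1). Discharge is the point at which such symptoms become reportable as AEs, and it is also where Protocol 11.7 stops counting non-serious ones.
- **Before inoculation.** The symptom-card exemption has not yet begun, so symptoms arising in the Unit at that time are AEs. They occur alongside swabs, nasal washes and blood draws, and must be assessed for relationship to the challenge. The SAP never places them in the Challenge phase.

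At stake are the by-group percentages of subjects with unsolicited AEs in each phase. With 22 challenged subjects per arm, one subject moved in or out of a table changes a percentage by 1/22 = 4.5 points.

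**Working it through.** The plan gives no figure to reproduce, so the check sets the windows side by side and then finds when events drop out.

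**Inputs.** Challenge is allowed 24 to 90 days after vaccination, with a target of 28 (Protocol 3.1). Unit entry is 1 or 2 days before challenge and planned discharge is Day 12. The SAP windows are those quoted above. Days are counted as calendar days with vaccination as Day 0, and a 28-day window includes Day 28.

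**Non-serious unsolicited AEs by time of onset**

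| Onset | Endpoint | Protocol 11.7 | SAP tables |
|---|---|---|---|
| Vaccination to Day 28, before Unit entry | in | in | in (vaccination) |
| Unit entry to inoculation, challenged by Day 28 | in | in; meets both of its windows | in (vaccination) |
| Unit entry to inoculation, challenged from Day 29 | in | in | partly or wholly listed only |
| Inoculation to discharge | in | in | in |
| Discharge to Day 28 after challenge | in | out; separate summary optional | in |

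The endpoint also names the time from consent to vaccination. Those events precede any exposure and are not part of this point.

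**Step 1: span left out by Protocol 11.7.** With discharge on Day 12, Days 13 to 28 are outside: 28 − 12 = 16 days, and 16/28 = 57% of the post-challenge window. Later discharge shortens this.

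**Step 2: pre-inoculation AEs under the SAP's 28-day rule.** Let C be the challenge day counted from vaccination, and L the lead time in the Unit (1 or 2 days). Pre-inoculation Unit time covers days C − L to C.

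- Some of it is outside the vaccination window once C > 28, that is from C = 29.
- All of it is outside once C − L > 28, that is from C = 30 (L = 1) or C = 31 (L = 2).
- For C = 24 to 28, none of it is lost; these AEs are in the vaccination tables.

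The allowed range holds 90 − 24 + 1 = 67 challenge days. All pre-inoculation AEs are listed only on 90 − 30 + 1 = 61 of them (L = 1) or 90 − 31 + 1 = 60 (L = 2). These are possible calendar days, not a share of subjects.

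**Step 3: the same with Table 2's 32 days as the limit.** Loss would begin at C = 33 and be complete from C = 34 (L = 1) or C = 35 (L = 2).

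**Step 4: reach of the 28- against 32-day difference.** Non-serious AEs are not collected after Day 28 from vaccination unless the subject is in the Unit. Days 29 to 32 overlap the pre-inoculation Unit days (C − 2 to C at most) only for C = 29 to 34. The difference can affect AE counts only for subjects challenged in that narrow range.

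**The case against.** The strongest reply is that the SAP controls the analysis. Protocol Section 11 describes itself as general and leaves detail to the SAP, and SAP 7.1.1 runs to Day 28 after challenge, where collection ends. This stands as far as it goes. A reader might infer that 57% of the post-challenge window will go unanalysed; the documents do not support that, because the SAP tabulates those days. What remains is that Protocol 11.7 contradicts the protocol's own endpoint and the SAP departs from it without saying so.

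Secondly, 28 and 32 days need not conflict. Table 2 structures periods for all safety data, and 7.1.1 can be read as a filter on unsolicited AEs within them. This stands. A reader might take the four extra days (4/28 = 14%) as a material discrepancy, but Step 4 shows that almost no non-serious AEs are collected then. Only an explicit statement of which rule governs is missing.

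Thirdly, starting the challenge period at inoculation is sound, since an event before inoculation cannot be caused by the virus. That justifies separating these events from post-inoculation ones, not leaving them out of every table when challenge is late.

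Finally, the loss is narrow: non-serious events, one or two days per subject, still listed, in a descriptive safety analysis. The long challenge window is meant for a few overflow subjects. All of this limits the size of the point but does not remove it.

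**Conclusion.** The point holds in a limited form: neither analysis section covers the endpoint window around challenge. Protocol 11.7 omits non-serious onsets from discharge to Day 28 after challenge, about 16 days. The SAP includes them as an undeclared change. The SAP in turn sends non-serious AEs between Unit entry and inoculation to listings only: in part from challenge Day 29, and entirely from Day 30 or 31. Subjects challenged by Day 28 lose nothing, and SAEs are tabulated throughout.

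A reader might infer from the 60 or 61 of 67 possible challenge days that most subjects are affected. The documents do not support that: the target is Day 28, and the later days exist mainly for overflow subjects.

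The conclusion rests on discharge at Day 12 and on the calendar-day counting given above. The number of AEs involved cannot be estimated, because the documents give neither AE rates nor a distribution of challenge days. This is worth correcting because it is cheap, not because it threatens the safety conclusions.

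**What to change.** 1. In Protocol 11.7, replace the quarantine-phase limit with Unit entry to 28 days after challenge, matching the endpoint and collection.
2. In SAP 7.1.1 and Table 2, keep the vaccination window for AE tables at 28 days after vaccination, or until inoculation if earlier. Tabulate AEs with onset from Unit entry to inoculation as a separate line for all challenged subjects, so that none is listed only. A footnote should say that for subjects challenged around the target day these AEs also appear in the vaccination table.
3. State that the 28-day filter in SAP 7.1.1 governs the unsolicited-AE tables, and that the 32 days in Table 2 only define periods.
4. Declare the change in SAP Section 2.

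The vaccination phase should not be ended at Unit admission. On the target schedule that is Day 26 or 27, whereas Protocol 9.2.6 and 12.1.2 require AEs to be examined for relationship to the vaccine up to Day 28.

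The cost is protocol and SAP wording, minor reprogramming of phase allocation and one extra table line. No new data are needed.

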11.8. Planned Analyses

The following analyses will be performed:

- PRIMARY ANALYSIS will be performed when all subjects have completed the quarantine phase or discontinued earlier. The pre-challenge neutralization and pre-F ELISA, and post-challenge RT-PCR, nasal mucous and tissue count, and clinical symptom data will be available although the analysis may be performed on snapshot data. All other data available at the time of primary analysis, including completed cellular data, will be included. Preliminary safety data, including Day 28 post-challenge, if available, will also be included.
- FINAL ANALYSIS will be performed when all subjects have completed the 6 month safety follow-up visit or discontinued earlier.

Depending on when the data are available, both analyses might be combined.

Additional interim analyses (blinded or unblinded) may be performed during the study for the purpose of informing future vaccine-related decisions in a timely manner, or upon health authority request. The results will not influence the conduct of the study in terms of early termination or later safety, efficacy or immunogenicity endpoint assessments, and will only be available to a selected group of sponsor personnel, excluding personnel involved in data management and data collection.

11.9. Data Review Committee

Data Review Committee

An internal DRC will be commissioned for this study, comprised of sponsor personnel not directly involved in the conduct of the study, who have expertise in clinical study conduct and vaccines. It will consist of at least one medical expert in the relevant therapeutic area and at least one statistician.

There are no planned DRC reviews. The DRC will only convene to discuss any significant or unexpected safety issues. The investigator and SRP will inform the DRC of any AE of concern.

After such a review, the DRC will make recommendations regarding the continuation of the study. The conclusions of the DRC will be communicated to the investigators, the IRB/IEC and the national regulatory authorities as appropriate. Details will be provided in a separate DRC charter.

If deemed necessary for safety review, the DRC may request the randomization codes and review unblinded data, if applicable.

